Table 1. Comparison simple and complex prevention on primary and secondary caries
reduction ^{***} .

		Complex Prevention			Simple Prevention			
Focus:	Intervention:		Fluoride Varnish		Interim Therapeutic Restoration	Toothpaste	Varnish	Silver Diamine Fluoride
1° Prevention	Smooth surface	25% ¹	40%²			25% ¹	40%²	
	Pits and fissure			80% ³				80% ⁵
2° Prevention	Arrest current caries				80%4			80% ⁵

* Efficacy estimates of caries reduction from systematic reviews of human randomized controlled trials.

**References: 1.¹¹⁻¹²; 2.¹³; 3.¹⁴⁻¹⁶; 4.^{14, 17-19}; 5.²⁰⁻²²

Both types of care will be provided to all children with active informed consent in grades PK - 8 (ages 5 – 14). Participating schools will be randomized or selected at the school level to receive either simple or complex prevention. All participants in a given school, community-based location, or at NYUCD will receive the same prevention as randomized. At the beginning of each school year, all students in grades PK - 8 will be given a personalized pre-populated principal recruitment letter, the parent/guardian alternate location recruitment letter, the parent/guardian informed consent form.

Electronic informed consent forms will be distributed to parents/guardians of new students who have not previously consented to see if they wish to have their child participate. Electronic informed consents can be distributed by the schools using whichever existing method the school uses for mobile phone contact, in emails, or on the school's social media page in the following ways:

- 1. NYU CariedAway Website URL by selecting "registering your child"
 - 1) English
 - https://dental.nyu.edu/faculty/epidemiology-health-promotion/pcori-grant.html
 - Short URL: https://dental.nyu.edu/pcori
 - 2) Spanish

https://dental.nyu.edu/faculty/epidemiology-health-promotion/pcori-beca.html

- 2. Hyperlinks in English and Spanish
 - English language eICF: https://is.gd/CariedAwayNYC
 - Spanish language eICF: https://is.gd/CariedAwayNYC_SP
- 3. CariedAway email toolkit in English and Spanish

The parent or legal guardian fills out the eICF and uses 'scratch' method (mouse, stylus, or finger) to sign and then returns the completed ICF via REDCap.

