3.2 Primary Study Endpoints

Caries arrest and prevention will be determined at each visit. The primary end point for caries arrest will be at 2 years, and follow on to termination of trial determine the length of time that caries remains arrested. The primary end point for caries prevention will be at 3 years, and follow on to termination of trial to determine stability of prevention.

Presence / absence of caries is assessed by visual/tactile methods. Sound tooth surfaces appear white and smooth. Active caries appear brown and soft. Arrested caries appear dark brown or black and hard.

For clinical assessment, we will train and standardize clinicians using validated criteria implemented by the Centers for Disease Control and Prevention (CDC) in the National Health and Nutrition Examination Surveys (NHANES). Training and validation were developed and documented by our Colleague, [name], while at the CDC and field tested in the examination of special athletes^{23,24}. Training and standardization of these examiners implement the World Health Organization guidelines^{25,26}.

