7.1 Sample Size Determination

The study is powered to the primary outcomes of caries arrest and caries prevention between twice-yearly simple and complex prevention. We expect to enroll approximately 14,100 students across the initial 60 schools over the duration of the study (N=235 per cluster). The remaining 16 schools will contribute approximately 3760 participants. From our pilot studies of school-based caries prevention, baseline caries prevalence is approximately 40%. Our power estimates assume an equal proportion of success, π , of 20% caries arrest. With a given non-inferiority margin (δ) of 10%, a total sample size per group of 198 (N_{tot} = 396) is required for an alpha of 5% and a power of 80%²⁹. However, as we use a cluster randomized design, this sample size is inflated to account for clustering (intraclass correlation coefficient = .10) by a design effect of 24.4 to a total required sample of 9,662.

For caries prevention, both interim therapeutic restorations and silver diamine fluoride have been shown to be 80% efficacious in individual clinical trials. Power for the repeated measures design was estimated using the method of Diggle et al (2002) for generalized estimating equations ³⁰. For power estimates, we control for the baseline prevalence of untreated decay. We assume a conservative average number of visits per child of 6, with a power of .80 and an alpha of 5%. We further assume a repeated measures correlation of 0.5 and a per-visit attrition rate of 20%. For a given minimally detectable effect size (standardized effect size difference) of .25, an attrition and clustering adjusted sample size of 12,874 is required. Thus, our study is powered for these conservative assumptions for caries prevention. Further, we note that in the presence of the nonlinear link function, ME-GLM is more powerful than GEE, thus our power estimates are conservative and the anticipated sample size is sufficient for analysis.

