7.2 Statistical Methods

For caries arrest, we will first determine the per-patient proportion of carious lesions treated with simple versus complex prevention that stayed arrested throughout the length of the study. The percentage of arrested caries (at the child level) will be modeled using multilevel binomial regression. Our noninferiority margin, δ , is set at 10%. Our null hypothesis is that simple prevention is not inferior to the complex prevention by at least δ : π_{simple} - $\pi_{\text{complex}} \ge \delta$. Our alternative hypothesis is that π_{simple} - $\pi_{\text{complex}} < \delta$. We will use differences in effect sizes as estimated by confidence intervals to determine clinical non-inferiority of the two prevention methods. For the prevention of new caries, we will use generalized estimating equations (GEE) with a logit link (caries prevalence) and a negative binomial link (caries incidence), assuming an exchangeable correlation matrix, to evaluate longitudinal effects of comprehensive care untreated decay. We will identify the number of teeth at risk for each child during each follow-up interval and determine the number of those teeth in which new caries is observed at the examination that ends that interval. Primary teeth lost in each interval and new permanent teeth will not contribute to data for that interval. To explore non-linear trends in untreated decay between simple and complex prevention, we will use generalized additive models (GAMs) with non-parametric smoothers. Longitudinal effects of simple and complex prevention on academic outcomes, compared to untreated children, will be analyzed using propensity score-matching and multilevel modeling. First, we will estimate propensity scores for each participant at baseline, establishing the probability of treatment assignment conditional on observed covariates (e.g., prior academic performance). Propensity scores will be used to match treatment students to students not receiving treatment, considering multiple forms of matching
such as nearest neighbor and caliper. Treated students and matched comparators will then be analyzed using multilevel mixed effects linear regression (for academic achievement) and Poisson regression (for school absences).

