7.3 Subject Population for Analysis

For study outcomes, participants will be analyzed using intent to treat. All participants will be analyzed as randomized in the original randomization, regardless of whether or not they received an intervention.

For dental-related service use and costs, all New York City elementary school-age children enrolled in Medicaid will be analyzed using intent-to-treat.

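### The primary arrest analysis uses one percentage per child with no follow-up term, so it need not estimate the 2-year difference on which the 10-point margin should be judged

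*Combined protocol and SAP*

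**What the plan says.** Section 7.2 first forms, for each child, the proportion of treated lesions that remain arrested over the length of the study. It then states: "The percentage of arrested caries (at the child level) will be modeled using multilevel binomial regression". The non-inferiority margin is 10 percentage points. No visit, time or follow-up-length term is named for this model.

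Section 3.2 has arrest determined at every visit and fixes the time point: "The primary end point for caries arrest will be at 2 years". Later follow-up is there to show how long arrest lasts. Section 3.1 says that children's first and second years supply the arrest data. Section 6.1.1 lets newly enrolled pupils join each year.

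On the analysis population, section 7.3 says: "All participants will be analyzed as randomized in the original randomization, regardless of whether or not they received an intervention". It gives no rule for a missing outcome. Section 8.11 excludes only visits with data errors that cannot be resolved.

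Section 7.1, in the paragraph on caries prevention, says: "We further assume a repeated measures correlation of 0.5 and a per-visit attrition rate of 20" percent. The arrest sample size carries no attrition allowance.

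**The concern.** A single percentage per child has no fixed time attached. A child last examined at 6 months and a child examined at 2 years would enter on the same footing, although their lesions have had very different times in which to lose arrest. Later entrants and children lost early make such differences certain to some degree. The plan deals with follow-up for new caries, where section 7.2 defines the teeth at risk interval by interval and uses GEE. The additional multilevel models in section 6.4 also concern incidence and prevalence. Arrest has no equivalent.

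Choosing 2 years over the whole study does not settle this, because children without a 2-year examination still have no stated treatment in the analysis. Arrest is one of the outcomes on which non-inferiority is to be declared. If the estimated contrast is not the 2-year difference, the 10-point margin is applied to a different quantity, and the rule chosen for incomplete children could decide the conclusion.

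**Working it through.** **The plan's own figure.** Inputs from section 7.1: success "of 20% caries arrest" in both arms, a margin of 10 points, and a sample size that "is required for an alpha of 5% and a power of 80" percent. Sidedness is not stated. With one-sided 5%, n per group = 2 × 0.20 × 0.80 × (1.645 + 0.842)² / 0.10² = 197.8, which matches "a total sample size per group of 198". One-sided 2.5% would give 252 and does not match. The design effect is 1 + (235 − 1) × 0.10 = 24.4, and 396 × 24.4 = 9,662. The implied standard error of the difference is 10 / (1.645 + 0.842) = 4.02 points.

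**Share without a 2-year examination.** Two visits a year make 2 years the fourth follow-up. Assume that the 20% loss per visit also applies to arrest, starts at the first follow-up and is permanent. Then 1 − 0.8⁴ = 59% lack that examination. Three or five follow-ups give 1 − 0.8³ = 49% or 1 − 0.8⁵ = 67%.

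**What last-seen scoring would estimate.** Among children with at least one follow-up, the shares last seen at 6, 12, 18 and 24 months are:
- 0.8 × 0.2 / 0.8 = 0.200
- 0.8² × 0.2 / 0.8 = 0.160
- 0.8³ × 0.2 / 0.8 = 0.128
- 0.8⁴ / 0.8 = 0.512

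Let p be 2-year sustained arrest in the complex arm and p − 0.10 that in the simple arm, with a constant failure risk per interval and equal loss in both arms. The deficit at follow-up k is p^(k/4) − (p − 0.10)^(k/4). The pooled deficit d is the weighted sum. The chance of declaring non-inferiority when the true 2-year deficit is exactly 10 points is Φ((10 − d)/4.02 − 1.645), holding the planned standard error.

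The value of p is uncertain in the documents. Section 7.1 uses 20%. Table 1 in section 3.1 gives 80% for arresting current caries in both arms, described as "Efficacy estimates of caries reduction from systematic reviews of human randomized controlled trials".

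| p at 2 years | Deficit at 6, 12, 18, 24 months | Pooled deficit d | False non-inferiority |
|---|---|---|---|
| 80% | 3.1, 5.8, 8.1, 10.0 | 7.7 | 14% |
| 65% | 3.7, 6.5, 8.5, 10.0 | 8.0 | 13% |
| 50% | 4.6, 7.5, 9.2, 10.0 | 8.4 | 11% |
| 25% | 8.5, 11.3, 11.3, 10.0 | 10.1 | 5% |
| 20% | 10.6, 13.1, 12.1, 10.0 | 10.9 | 3% |

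If the standard error comes from the planned enrolment instead, with an effective 30 × 235 / 24.4 = 289 children per arm, the first and last rows become about 17% and 3%.

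**Other rules.** Scoring unseen lesions as failures, with equal loss in both arms, gives 0.8⁴ × 10 = 4.1 points and Φ((10 − 4.1)/4.02 − 1.645) = 43%. Dropping children who are missing completely at random leaves 10.0 points and 5%. A deficit that is constant from the first follow-up also stays at 10.0 under last-seen scoring.

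**The case against.** The strongest reply is that the plan states no scoring rule, so any bias comes from a rule supplied by the reader. This stands as far as direction goes. A reader might infer that the analysis shrinks a true deficit towards non-inferiority. The documents do not support that: neither last-seen nor failure scoring is written anywhere, and at the section 7.1 arrest figure of 20% last-seen scoring enlarges the deficit. The 4.1 points and 43% in particular rest on a rule that the plan never states. A single percentage could also be completed by imputation or weighting.

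The 59% is borrowed as well. The attrition rate belongs to the prevention calculation, where the assumptions are called conservative. Permanent loss is doubtful too. Over ten twice-yearly visits it would give (1 − 0.8¹⁰)/0.2 = 4.5 visits attended on average, while section 7.1 assumes an average of 6 visits per child. If those are visits attended, the two do not fit. Consent lasts up to 5 years, so a child who misses a visit can return. The 59% is an illustration, not a forecast.

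Nor does dropping incomplete children plainly breach section 7.3, which can be read as governing arm assignment rather than missing outcomes.

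Finally, modelling current status at each visit would replace sustained arrest with point-in-time arrest: a lesion that reactivates and is arrested again would change from failure to success. That is right, and the remedy must avoid it.

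None of this supplies the missing follow-up term. It limits what can be said about direction and size.

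**Conclusion.** The point holds as a mismatch between the endpoint and its analysis. The primary arrest endpoint is at 2 years. The analysis is one percentage per child over the study, with no follow-up term and no handling of children without a 2-year examination. As written, it mixes follow-up lengths and need not estimate the difference to which the margin should apply.

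The size depends on assumptions outside the plan's text. With last-seen scoring, constant failure risk and 20% permanent loss per visit in both arms, a true 10-point deficit appears as anything from 7.7 to 10.9 points as complex-arm arrest runs from 80% to 20%. False non-inferiority then runs from about 14% to 3%, against a nominal 5%. A claim that every deficit at or beyond the margin would be hidden goes too far: under last-seen scoring, a 15-point deficit growing linearly over the four follow-ups pools to 11.1 points, still outside the margin. What is established is that the plan leaves open a choice that can move the estimate across the margin.

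**What to change.** In section 7.2, replace the single child percentage with each entry lesion's record at every examination up to 2 years. Score a lesion as a success only while it has been arrested at all examinations so far, so that sustained arrest remains the outcome. Keep the multilevel binomial family (lesion within child within school) and add visit and arm-by-visit terms, for example as a discrete-time model of first loss of arrest. Judge the 10-point margin on the model-based simple-minus-complex risk difference at 2 years.

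Let children lost early contribute only the examinations they had. Do not carry the last status forward or count unseen lesions as failures. State that children with no follow-up examination contribute no outcome data to this model, and that it assumes loss is unrelated to later arrest given what was observed. State also how intermittently missed examinations and shed primary teeth enter.

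Add one tipping-point analysis that lowers arrest after loss in the simple arm, including children who never return, and report where non-inferiority fails.

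The data are already recorded at each visit, so the cost is SAP wording, more model code and a somewhat wider 2-year interval.

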2.1 Primary Objective

To determine if simple prevention is non-inferior to complex prevention for caries arrest and longitudinal caries prevention.

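### The non-inferiority hypotheses for caries arrest are reversed: as printed, the test is passed more easily the worse simple prevention performs

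*Combined protocol and SAP*

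**What the plan says.** Section 2.1 sets the aim: "To determine if simple prevention is non-inferior to complex prevention for caries arrest and longitudinal caries prevention".

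Section 7.1 fixes the direction of the parameter: "Our power estimates assume an equal proportion of success, π , of 20% caries arrest". Section 7.2 models the same quantity: "The percentage of arrested caries (at the child level) will be modeled using multilevel binomial regression". On both descriptions a larger π is a better result.

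Section 7.2 then gives the hypotheses, with δ = 10%. In words: "Our null hypothesis is that simple prevention is not inferior to the complex prevention by at least" δ. In symbols, the null is π_simple − π_complex ≥ δ and the alternative is π_simple − π_complex < δ. The next sentence says that confidence intervals for differences in effect size will decide non-inferiority. It gives no confidence level, no side and no limit to compare with the margin. No other section restates the hypotheses.

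**The concern.** In a non-inferiority trial the null must be that the new treatment is worse by at least the margin, so that rejecting it supports the claim. Section 7.2 departs from this in two ways that also contradict each other.

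- **Words.** Read literally, the null is that simple is not inferior by δ or more. Rejecting it would show that simple is inferior.
- **Symbols.** With π a success proportion, the null is that simple is better by at least 10 points. The alternative covers a smaller advantage, equality and inferiority of any size. Rejecting the null shows only that simple is not better by 10 points or more.

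This is the only formal decision rule for caries arrest, a primary outcome. Sections 1.2 and 1.4.3 would use a finding of equal effectiveness to argue for wider use of simple prevention, because it takes about a quarter of the time and cost. A rule that can be met by a clearly inferior result cannot support that argument. Leaving the bound unstated also leaves it open to choice after the data are seen.

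**Working it through.** **Inputs.** From 7.1: π = 0.20 in both arms, δ = 0.10, alpha 5% (side not stated), power 80%, 198 per group, 235 children per school, ICC 0.10, design effect 24.4, total 9,662. From 7.2: the hypotheses above.

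**Step 1: reproduce the plan's sample size.**

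n per arm = (z_alpha + z_power)² × 2π(1 − π) / δ²

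- One-sided 5%: (1.645 + 0.842)² × 2 × 0.2 × 0.8 / 0.10² = 197.8, so 198 per arm and 396 in total. This matches.
- One-sided 2.5%: 252 per arm. This does not match.
- Design effect: 1 + (235 − 1) × 0.10 = 24.4, and 396 × 24.4 = 9,662. This matches.

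The plan's alpha is therefore one-sided 5%. The formula depends on π only through π(1 − π), so 0.20 and 0.80 give the same n. The arithmetic cannot show whether π is success or failure; only the wording of 7.1 and 7.2 does that.

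**Step 2: chance of passing each rule.** Let d = π_simple − π_complex and SE = √[π_s(1 − π_s)/198 + π_c(1 − π_c)/198], with π_c = 0.20 and a normal approximation.

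- Printed symbolic rule (reject d ≥ +0.10): Φ((0.10 − d)/SE − 1.645)
- Standard rule (reject d ≤ −0.10): Φ((d + 0.10)/SE − 1.645)

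Example, simple 10%: SE = √[(0.09 + 0.16)/198] = 0.0355. Printed: Φ(0.20/0.0355 − 1.645) = Φ(3.98), above 99.9%. Standard: Φ(0 − 1.645) = 5.0%.

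| True arrest, simple | d (points) | Printed rule | Standard rule |
|---|---|---|---|
| 5% | −15 | >99.9% | 0.07% |
| 10% | −10 | >99.9% | 5.0% |
| 15% | −5 | 98.9% | 37.0% |
| 20% | 0 | 80.0% | 80.0% |
| 25% | +5 | 32.6% | 97.4% |
| 30% | +10 | 5.0% | 99.9% |

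The two rules agree only at d = 0, the point at which the sample size was calculated. That is why 198 reproduces despite the reversal.

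**Step 3: sensitivity.**

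- At one-sided 2.5% and d = −10 points, the printed rule passes more than 99.9% and the standard rule 2.5%.
- Suppose only children with caries contribute: 40% of 235 = 94 per school, 30 schools per arm, design effect 1 + 93 × 0.10 = 10.3, effective n = 30 × 94 / 10.3 = 273.8 per arm. Then 10% vs 20% gives >99.9% against 5.0%, and 30% vs 20% gives 5% against >99.9%. An assumed 60% vs 80% gives about 100% against 0.001%.

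**Step 4: one observed result.** With 5% vs 20% observed and 198 effective per arm, the 90% interval for d is −20.3 to −9.7 points. Its upper limit is below +10, so the printed rule is met. Its lower limit is below −10, so non-inferiority is not shown. The whole interval lies below zero, so the data point to inferiority.

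**The case against.** The best defence is that this is a labelling slip. Table 1 gives 80% arrest for both interim therapeutic restorations and silver diamine fluoride, and its complement is the 20% used for π in 7.1. If π was meant as the proportion of lesions not arrested, both printed inequalities are correct. That is plausible, and the authors should confirm the scale. But it contradicts the text of 7.1 ("Our power estimates assume an equal proportion of success") and the outcome modelled in 7.2, and the verbal null would still be inverted.

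It can also be said that the objective is stated consistently elsewhere, that the operative step is the confidence-interval sentence, and that no sensible analyst would apply the symbols mechanically. The intent is indeed clear, and the pass rates above apply to the symbolic rule only; the words describe a different test. But the interval sentence names no level, side or bound, so it does not supply the missing rule.

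The inputs in Step 3 are partly assumed: 94 contributing children per school with no attrition, and the 60% vs 80% scenario. The direction of the error depends on none of them.

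**Conclusion.** The hypotheses are wrong as written. On the success scale that the plan defines, neither the words nor the symbols form a valid non-inferiority test, and they disagree with each other. If the printed inequality were applied, a true 10-point deficit at 20% arrest on complex would pass in more than 99.9% of trials instead of 5.0%, and a true 10-point advantage would pass in 5.0% instead of 99.9%. These figures assume 198 effective children per arm, one-sided 5% and a normal approximation. The pattern is the same at one-sided 2.5% and in the other scenarios tried. The error lies in the decision rule for caries arrest; the sample size is unaffected. It must be corrected because it governs a primary outcome.

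**What to change.** In 7.2, with π defined as the proportion of lesions arrested, write:

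- H0: π_simple − π_complex ≤ −10 percentage points
- H1: π_simple − π_complex > −10 percentage points
- Non-inferiority is declared only if the lower confidence limit for π_simple − π_complex lies above −10 points.

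Replace the verbal null so that it says simple is worse than complex by 10 points or more. State the confidence level. The planned 198 per arm corresponds to one-sided 5%, that is, a two-sided 90% interval.

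If the authors did mean non-arrest, the equivalent repair is to relabel π in 7.1 and 7.2, keep the inequalities, correct the verbal null and require the upper limit to lie below +10 points.

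Either repair is an edit to the text, with no new data and no change in conduct. At one-sided 5% the sample size stays at 198 per arm (9,662 after clustering). Choosing one-sided 2.5% would instead need 252 per arm: 504 × 24.4 = about 12,298 in total.

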For the purposes of the analysis on dental-related service use and costs among Medicaid beneficiaries, all children participating in Medicaid of elementary school age will be included in the analysis, except for children in participating schools that do not provide informed consent to provide oral health and Medicaid dental service use data.

The Primary Specific Aims are to:

- 1. Determine the non-inferiority of simple vs complex caries prevention for preventing new caries (primary prevention).
- 2. Determine the non-inferiority of simple vs complex caries prevention for arresting current caries (secondary prevention).
- 3. Determine the impact of simple vs complex prevention on child oral healthrelated quality of life
- 4. Determine the impact of once per year vs twice per year care on the arrest and prevention of caries

Notably, toothaches or office based dental care reduces in-class learning time. If the caries prevention programs are as effective as predicted, knowing the time/trade-off will be important. Thus a secondary outcome of the study will be school performance (school absence and student achievement). To insure accurate assessments, program participants will be compared to children in their own schools and to children in NYC "peer schools" not participating in the study. No additional data is collected for educational outcomes from participants.

The Secondary Specific Aims are to:

- 1. Determine the impact of prevention vs no prevention on school absence
- 2. Determine the impact of prevention vs no prevention on standardized test performance
- 3. Determine the impact of simple vs complex prevention on school absence and test performance

The exclusion criteria will be those: (1) not attending participating schools, (2) those attending participating schools without informed consent, or (3) those attending participating schools with informed consent, but without assent and (4) those allergic to silver.

For the purposes of the analysis on dental-related service use and costs among Medicaid beneficiaries, the only excluded groups are (1) children not participating in Medicaid will be excluded and (2) children participating in Medicaid in Caried*Away* schools, but without informed consent to provide oral health and Medicaid dental service use data.

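### Aim 1 (preventing new caries) has two outcomes and no rule for which decides non-inferiority; one of them, caries prevalence, does not measure new caries

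*Combined protocol and SAP*

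**What the plan says.** Section 1.2 sets Aim 1 as: "Determine the non-inferiority of simple vs complex caries prevention for preventing new caries (primary prevention". Arrest of existing caries is a separate primary aim (Aim 2).

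Section 7.2 assigns two models to Aim 1 in one sentence. The first: "For the prevention of new caries, we will use generalized estimating equations (GEE) with a logit link (caries prevalence". The second: "a negative binomial link (caries incidence), assuming an exchangeable correlation matrix". It then defines how new disease is counted: "We will identify the number of teeth at risk for each child during each follow-up interval", and from these "determine the number of those teeth in which new caries is observed at the examination that ends that interval". Primary teeth lost and permanent teeth gained during an interval are left out of that interval.

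Other sections bear on the choice between the two:
- Section 3.2 puts the prevention endpoint at 3 years but names no measure for it.
- Section 6.4 carries prevalence and incidence side by side through all GEE and multilevel models, for all teeth, adult teeth and deciduous teeth.
- The 10% margin appears in the caries-arrest text of Sections 7.1 and 7.2. No margin is given for prevention on either measure.
- Section 7.1 says that "baseline caries prevalence is approximately 40" per cent. Baseline decay is controlled for in the power estimates there, but it is not among the confounders named in Section 6.4.
- Section 6.1.6 has the examiner record active and arrested decay and filled surfaces. No section says whether an arrested or restored lesion counts towards caries prevalence.

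**The concern.** All consenting children in participating schools are enrolled, whether or not they have decay (Study Summary). A child who enters with a lesion that is never arrested is prevalent at every later visit without any new disease. A child whose lesion is restored or shed, or is arrested if arrested lesions are not counted, becomes non-prevalent, whatever happened to the sound teeth. Prevalence therefore mixes Aim 1 with Aim 2 and with tooth turnover between ages 5 and 14.

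In a non-inferiority comparison, anything that shrinks a true difference makes the claim easier to reach. Because neither outcome has priority, the two could disagree at 3 years and the prevalence result could still be used to support Aim 1.

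**Working it through.** **The plan's own figures.** The plan gives no figure for how prevalence relates to new caries, so none is disputed. The arrest sample size supplies one input and reproduces. With "an alpha of 5% and a power of 80" per cent, success of 20% in both arms, a margin of 10 points and a one-sided test: (1.645 + 0.842)² × 2 × 0.2 × 0.8 / 0.1² ≈ 198 per group. The design effect is 1 + 234 × 0.10 = 24.4, and 396 × 24.4 = 9,662. The prevention sample of 12,874 can be neither confirmed nor faulted, because the attrition step is not given. A standard repeated-measures formula (two-sided 5%, 6 visits, correlation 0.5, effect size 0.25) gives about 7,150 after clustering and before attrition.

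**Inputs for the check**
- Caries at entry, b = 0.40 (Section 7.1).
- Arrest, a: Section 7.1 assumes an equal proportion "of 20% caries arrest"; Table 1 in Section 3.1 gives 80% for each arm's arresting agent.
- Risk of any new caries in a child, I: 0.20 complex and 0.30 simple. These are assumptions, as is independence from caries at entry; the documents give no such figures.
- Arrested lesions are taken as not counted in prevalence, except in the counting example below.

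**Formula.** Child-level prevalence is P = 1 − [1 − b(1 − a)](1 − I). With equal arrest, the difference between arms is [1 − b(1 − a)] × (I_simple − I_complex). The true deficit is 10 points, odds ratio (0.3 × 0.8)/(0.7 × 0.2) = 1.71.

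| Arrest, complex / simple | Prevalence, complex | Prevalence, simple | Difference (points) | Odds ratio |
|---|---|---|---|---|
| 0% / 0% | 52.0% | 58.0% | 6.0 | 1.27 |
| 20% / 20% | 45.6% | 52.4% | 6.8 | 1.31 |
| 80% / 80% | 26.4% | 35.6% | 9.2 | 1.54 |
| 20% / 30% | 45.6% | 49.6% | 4.0 | 1.17 |
| 20% / 40% | 45.6% | 46.8% | 1.2 | 1.05 |
| 80% / 60% | 26.4% | 41.2% | 14.8 | 1.95 |

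At the plan's 20% arrest, the carried-over share is 0.40 × 0.80 = 32%, so the multiplier is 0.68. At 80% arrest the carried-over share is 8% and the multiplier 0.92. Under equal arrest, 10-point deficits of 10% vs 20% and 30% vs 40% give the same differences in points.

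**Cancellation.** Setting the two prevalences equal gives the arrest that simple would need: about 44% if complex arrests 20%, and about 79% if complex arrests 50%. If complex arrests 80%, the solution exceeds 100%, so cancellation is impossible.

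**Counting rule.** Suppose new caries is 20% in both arms, 80% of complex lesions are restored and not counted, and every arrested lesion under simple prevention is still counted. Prevalence is then 1 − 0.92 × 0.80 = 26.4% for complex and 1 − 0.60 × 0.80 = 52.0% for simple, a 25.6-point gap with no difference in new caries.

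**Incidence.** A count of new caries in teeth at risk contains no carried-over lesions and does not respond to their arrest, so this mechanism does not touch it.

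**The case against.** The strongest reply is that the plan already has the right analysis. Incidence on teeth at risk is named for the same aim in the same sentence, and it would show the deficit. A reader who stopped at the prevalence model might infer that Aim 1 is analysed by prevalence alone; Sections 7.2 and 6.4 show otherwise. This reply stands, and it reduces the point to one of priority. It does not remove the point, since no section makes incidence decisive.

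A reader might also infer that prevalence would hide a real deficit altogether. The documents do not support that. The plan assumes equal arrest, at 20% in Section 7.1 and 80% in Table 1, and near-cancellation needs simple to arrest far more than complex. Equal arrest is, however, what Aim 2 sets out to test, so Aim 1 should not depend on it.

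Nor does the error always favour simple: the 80% / 60% row and the counting example run against it. And because the 10% margin is stated for arrest only, these differences cannot be read against a 10-point limit for prevention.

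The formula lets old lesions leave only through arrest. If half of the 32% carried over had been shed or restored, the multiplier would be 0.84 and the deficit would show as 8.4 points. The adult-teeth analysis and adjustment for dental treatment help in part. Neither removes unarrested baseline lesions in permanent teeth.

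Finally, untreated decay matters to the stakeholders (Section 1.1.3). That is a reason to report it, though not as the test of Aim 1.

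**Conclusion.** The point holds as one about unstated priority between two outcomes, one of which does not match the aim. With equal arrest between 0% and 80%, the assumed 10-point deficit in new caries shows as 6.0 to 9.2 points in prevalence, a loss of 8% to 40%; at the plan's 20% arrest it is 6.8 points. This dilution favours non-inferiority. With unequal arrest or an uneven counting rule, the direction is not fixed.

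The sizes rest on the plan's 40% at entry and on assumed new-caries risks independent of caries at entry. Dilution is larger if the excess of new caries falls mainly on children who already had lesions, and smaller if it falls mainly on the others. Because a sound incidence analysis is already written into the plan, this is a cheap improvement rather than a fundamental flaw.

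**What to change.** In Section 7.2, state that incident caries in teeth at risk, as already specified there, is the sole deciding outcome for Aim 1 at the 3-year endpoint of Section 3.2. Keep prevalence of untreated decay as a secondary combined outcome, and say that it cannot support the Aim 1 non-inferiority claim. State there whether arrested and restored lesions count towards it. If a logit GEE is kept for Aim 1, define its outcome as any new caries in teeth previously recorded as sound.

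The cost is a short change of text. Section 6.1.6 already records the status of all teeth at examination, so no new data are needed. The downside is somewhat fewer events than prevalence would give.
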